### **5.6.1.2. Analysis of Adverse Events**

Safety analyses will be performed on the FAS. Continuous variables will be summarized using the following statistics, as appropriate: number of observations, median, minimum, and maximum. Frequencies and percentages (one decimal place) will be generated for categorical variables. No formal comparisons between groups will be provided.

Safety data will be analyzed and presented by study intervention and phase. Denominator for the percentages is the number of participants in the considered population and phase for a certain regimen (incidence per 100 participants/phase).

Number and percentage of participants with at least one particular AE (unsolicited/solicited) will be tabulated. Unsolicited AEs will be summarized by System Organ Class and Preferred Term. Solicited AEs will be summarized by class (administration site, systemic) and preferred term.

For solicited AEs, the following tables will be provided: summary, by worst severity grade, at least grade 3, related (systemic only), time to onset (in days) and duration (in days). Note: Duration is defined as number of days from the start of the event until resolution of the event. The time to first onset is defined as (date of first onset – reference date + 1). The reference date is the start date of the vaccination period.

A tabulation of the distribution of temperatures per half degree intervals will also be provided.

For unsolicited AEs, the following tables will be provided: summary table (including SAE, fatal outcome, discontinuation and AESI), all events, most frequent, at least grade 3, permanent stop of vaccine, related, SAE, related SAE, potential AESI and AESI.

Unsolicited non-serious adverse events collected outside the 28-day period following the vaccination will be presented through listings.

Listings and/or participant narratives will be provided as appropriate, for those participants with a fatal outcome, discontinue study vaccinations due to an AE, discontinue study due to an AE, or experienced a severe SAE, or an AESI event.

### **5.6.1.3. Phase Allocation of Adverse Events**

For this study, 3 phases are defined: screening, treatment and follow-up.

As the analysis of solicited events will be based on the overall assessment of the investigator which is documented in the CE domain, the Analysis Data Model (ADaM) dataset will be based on the CE domain. Solicited events are allocated to the phases as described below, however they are always allocated to the respective post-dose period and will never be attributed to the screening phase. Time of day is not considered while attributing solicited AEs to phases.

For unsolicited AEs, the steps below are followed as well.

#### Step 1: Allocation of events to the periods:

Adverse events in the SDTM (Study Data Tabulation Model) database are allocated to periods based on their start date/time. If the start date/time of an event falls between (or on) the start and stop date/time of a period, the AE is attributed to that period (treatment-emergent principle).

- In case of partial start or stop dates (i.e. time and/or day and/or month and/or year missing), the events are allocated to the periods using the available partial information on start and end date; no imputation will be done. If, for instance, the AE start date only month and year are available, these data are compared to the month and year information of the periods. This rule may lead to multiplication of the event as a consequence of its assignment to multiple periods.
- In case of a completely missing end date, the date is imputed by the cut-off date of the analysis for participants still ongoing in the study, and by the end date of the last period for participants who discontinued or completed the trial. The imputed end dates will not be shown in the data listings. In case of a completely missing start date, the event is allocated to the first active phase (post dose 1 period), except if the end date of the AE falls before the start of the first active phase (post dose 1 period).

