## 1.2. Study Design

This is a randomized, double-blind, parallel, multicenter, interventional study in healthy (including stable comorbidities) adults  $\geq 18$  years of age. In this study, the safety, reactogenicity, and immunogenicity of Ad26.COV2.S co-administered with a seasonal influenza vaccine will be evaluated.

Participants will be randomized in parallel in this study. Participants aged  $\geq 65$  will be randomized in a 1:1:1:1 ratio to 1 of 4 groups. Participants aged  $\leq 64$  will be randomized in a 1:1 ratio to 1 of 2 groups (Group 1 or Group 2). Efforts will be made to ensure good representation in terms of race, gender, and ethnicity.

Participants will receive Ad26.COV2.S and a seasonal quadrivalent (*standard-dose* or *high-dose*) influenza vaccine either concomitantly on Day 1 and placebo on Day 29 (co-administration groups 1 and 3) or a seasonal quadrivalent (*standard-dose* or *high-dose*) influenza vaccine and placebo on Day 1 and Ad26.COV2.S on Day 29 (control groups 2 and 4) (see table 2 below).

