### 5.1.2. Study phases

The phases in the study will be considered as follows:

Phase	# Phase	Period	# Period	Interval	
				From	To
Screening	1			Date and time of signing the informed consent form	One minute prior to start of post-dose period
Post-dose	2	Post- dose 1	1	Date and time of the first vaccination	Minimum of:  a) 23:59 at the date of last contact (for early discontinuation)  b) 23:59 at the database cut- off date for analyses conducted before the final analysis  c) 23:59 on 28 days after the first vaccination (23:59 of day of vaccination + 28 days)  d) One second prior to post- dose 2. If a participant discontinued from the second vaccination, then the maximum of (28 days after the first vaccination at 23:59, scheduled visit 28 days after

					first vaccination at 23:59) will be used
Follow-up 1	3			One minute after Post dose 1 period end	
Minimum of:
 
a) 23:59 at the date of last contact (for early discontinuation)
 
b) 23:59 at the date of database cut-off date in case of interim analysis
 
c) One minute prior to post dose 2

Post-dose	2	Post-dose 2	2	Date and time of the second vaccination	
Minimum of:
 
a) 23:59 at the date of last contact (for early discontinuation)
 
b) 23:59 of day of second vaccination + 28 days

Follow Up 2	4			One minute after Post-dose 2 period end.	
Minimum of:
 
a) 23:59 at the date of last contact (for early discontinuation or participants that completed the study)
 
b) 23:59 at the database cut-off date for analyses conducted before the final analysis

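### For unsolicited AEs with an incomplete start date, the period-allocation rule can count one event in two periods, or in Control move it out of the Ad26.COV2.S period

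*SAP*

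**What the plan says.** SAP 5.6.1.3 Step 1 places an AE in the period that contains its start date and time. For incomplete dates, where a missing time is enough to qualify, "the events are allocated to the periods using the available partial information on start and end date; no imputation will be done". The SAP states the consequence itself: "This rule may lead to multiplication of the event as a consequence of its assignment to multiple periods".

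For events without any start date: "In case of a completely missing start date, the event is allocated to the first active phase (post dose 1 period"), with one exception, "except if the end date of the AE falls before the start of the first active phase".

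Solicited events are carved out in the opening text of 5.6.1.3: "however they are always allocated to the respective post-dose period and will never be attributed to the screening phase". Unsolicited events get no such protection: "For unsolicited AEs, the steps below are followed as well".

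The period limits are in SAP 5.1.2. Post-dose 1 ends at the earliest of several limits. The two that matter here are "23:59 on 28 days after the first vaccination" and one second before post-dose 2 begins. Post-dose 2 begins at the date and time of the second vaccination.

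The two periods carry different products. Control participants receive "influenza vaccine and placebo on Day 1 and Ad26.COV2.S on Day 29 (control groups 2 and 4"). CoAd participants receive both vaccines on Day 1 and placebo on Day 29.

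**The concern.** SAP 5.6.1.2 presents safety by intervention and phase, as the number and percentage of participants with at least one event. In Control, the period stands in for the vaccine: post-dose 1 is influenza vaccine plus placebo, and post-dose 2 is Ad26.COV2.S. Assigning an event to the wrong period therefore attributes it to the wrong vaccine.

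Two separate things can go wrong for an unsolicited AE that follows Ad26.COV2.S in Control. With a partial start date it can be copied, so that it also appears under influenza vaccine plus placebo. With no start date it is moved, so that it appears only there. Safety of separate against concomitant administration is a stated secondary objective, and the unsolicited tables include related events, SAEs and AESIs. The SAP gives no tie-break and no count of the events affected.

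**Working it through.** The documents give no figure for this rule, so there is none to reproduce. The check applies SAP 5.1.2 and 5.6.1.3 to calendar dates.

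**Inputs.** The dose 2 window is -3/+7 days around Day 29, that is Day 26 to Day 36 (protocol 1.3.1). Period limits are from SAP 5.1.2. Allocation and combination rules are from SAP 5.6.1.3.

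**Case 1: onset on the day of dose 2, time missing.**
- Dose 2 on Days 26 to 29: the 28-day limit falls at 23:59 on Day 1 + 28 = Day 29. One second before dose 2 is earlier, so post-dose 1 ends on the calendar day of dose 2. Post-dose 2 starts that same day. The date matches both periods.
- Dose 2 on Days 30 to 36: post-dose 1 has already closed at 23:59 on Day 29. The date matches follow-up 1 and post-dose 2. This matters less, because non-serious unsolicited AEs outside the 28 days go to listings (SAP 5.6.1.2).

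**Case 2: only month and year known.** A true onset after dose 2 also matches post-dose 1 if its month is one that post-dose 1 touches. I assume Day 1 dates uniform over 365 days from 1 October 2021, uniform onset lags, and an end date that does not rule out the earlier period. The share is then close to 1 - (mean days from the end of post-dose 1 to onset) / (mean month length), with mean month length 365/12 = 30.4 days.

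| Dose 2 | Onset 0-6 days after | Onset 0-28 days after |
|---|---|---|
| Day 26 or 29 | 1 - 3/30.4 = 0.901 | 1 - 14/30.4 = 0.540 |
| Day 36 | 1 - (7+3)/30.4 = 0.671 | 0.325 |

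The last cell comes from a day-by-day count. The simple formula gives 1 - 21/30.4 = 0.309, which is slightly low because the share cannot fall below zero at the longest lags. The day-by-day count gives the same values as the formula in the other cells. These are shares of month-only events, not of all events.

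**Case 3: no start date.** The event is placed in post-dose 1 alone, unless it ended before that period. It is moved, not duplicated.

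**Does Step 2 repair the copies?** No. Its fourth rule keeps events that start in two consecutive active periods as separate AEs. Its first remark allows combination only where start and stop dates are known.

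**Who is touched.**
- Solicited AEs: none.
- Control: an unsolicited AE after Ad26.COV2.S can be copied or moved back to influenza vaccine plus placebo.
- CoAd: an unsolicited AE after the Day 29 placebo can be copied or moved back to the co-administration period.
- Both arms: a month-only AE that follows Day 1 can be copied forward.

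**Effect on tabulated percentages.** This would need the frequency of missing times, month-only dates and missing dates among unsolicited AEs. The documents give none of these, so it cannot be computed.

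**The case against.** The SAP discloses the multiplication, applies the same rule to both arms, makes no formal safety comparison, and tabulates participants rather than events. A copy therefore adds at most one participant per period and term. Fully dated events are allocated correctly, and protocol 10.3.8 and 10.3.9 provide for queries that may complete many dates. All of this stands, and it limits the consequence. It does not remove the defect: no text says which period wins when the date fits two.

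Three stronger readings are tempting, and the documents do not support them.

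- *Ad26.COV2.S reactogenicity is miscounted.* Solicited local and systemic events are always allocated to their own post-dose period, so the reactogenicity tables are untouched.
- *The rule makes co-administration look better than influenza vaccine alone.* Control post-dose 1 can gain events that followed Ad26.COV2.S, but CoAd post-dose 1 can gain events that followed placebo, which pushes the other way. The net direction is not established. Partially dated events also stay in Control post-dose 2, so that column loses only undated events.
- *A bias in percentage points can be read off protocol Table 1.* Chills, arthralgia, malaise, asthenia, muscular weakness and pain in extremity give (67+35+26+18+10+9)/3,356 = 165/3,356 = 4.9%. These terms can occur in one person, so the share with any of them lies between 67/3,356 = 2.0% and 4.9%. It would then have to be multiplied by the unknown share with onset on the day of dose 2 and no recorded time, among participants with dose 2 on Days 26 to 29 only.

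**Conclusion.** The point holds for unsolicited AEs with incomplete start dates. With dose 2 on Days 26 to 29, an event dated that day without a time is assigned to both post-dose periods. In Control this can tabulate an AE after Ad26.COV2.S under influenza vaccine plus placebo as well. An undated event goes to post-dose 1 unless it ended earlier, so in Control one that followed Ad26.COV2.S is lost from the Ad26.COV2.S period.

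The size is unknown. It depends on how often dates are incomplete and, for the same-day case, on how often the onset time is recorded. The month-only shares in the table rest on the uniformity assumptions given with it. The primary immunogenicity analysis is unaffected. This is a repair to a descriptive analysis, worth making because it costs almost nothing and because period identifies vaccine in Control.

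**What to change.** In SAP 5.6.1.3 Step 1, add one rule: *an unsolicited AE whose onset date equals a vaccination date and whose onset time is missing is assigned only to the post-dose period that starts with that vaccination.* This also removes the copies into follow-up 1 for later dose 2 dates, and into screening for Day 1 events.

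The rule agrees with what the SAP already does elsewhere. Solicited AEs are allocated without regard to time of day (5.6.1.3), and analgesics taken on the vaccination day go to the post-dose period even if taken before the injection (Appendix 5).

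In the by-period tables, footnote the number of events assigned to more than one period and the number placed by the missing-start-date rule, so that a reader can judge their weight.

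Do not add a default that sends month-only or undated events to whichever period follows Ad26.COV2.S. That would depend on the arm, could never credit such an event to influenza vaccine alone, and would build in a bias of the opposite kind.

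The cost is one sentence, a small programming change and a footnote. The downside is small: an event that truly began earlier on the vaccination day is attributed to that vaccination.

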#### Step 2: Combination of events:

Overlapping/consecutive events are defined as events of the same participant with the same preferred term which have at least 1 day overlap or for which the start date of an event is 1 day after the end date of the preceding event. Overlapping/consecutive events may be combined into one AE or not, according to the following rules:

- 1) If overlapping/consecutive events start in one of the following phases/periods - Screening or Follow-up (defined as non-active periods) - followed by an AE in - Post-dose period (defined as active period) - they are allocated to their respective phases/periods and are considered as separate events.
- 2) In case overlapping/consecutive events start within a single period, they are considered as one and the same AE. The individual events which contribute to this AE are retained as

individual records in the ADaM database but are assigned the same onset, period, and total duration. All related attributes to the AE/phase/period should also be consistent with the new event.

- 3) In case overlapping/consecutive events start in both an active period followed by a consecutive non-active period, they are allocated to the active period only and are considered as one and the same AE. The individual events which contribute to this AE are retained as individual records in the ADaM database but are assigned the same onset, treatment period, and total duration. All related attributes to the AE/phase/period should also be consistent with the new event.
- 4) In case an active period is followed by another active period, and the overlapping/consecutive events start in both periods, they are allocated to their respective period and are considered as separate AEs. In case overlapping/consecutive events start in non-consecutive periods (regardless of active or non-active), they are allocated to their respective period and are considered as separate AEs.

Remarks:

1. Events can only be combined into one and the same AE if their start and stop dates are known.
2. In case the completely missing end date is imputed (for period allocation), this date is also considered as a complete date.
3. Time is not considered when determining overlap of events.

#### **5.6.1.4. Missing Adverse Event Data**

Missing data will not be imputed. Participants who do not report an event will be considered as participants without an event. An AE with a missing severity or relationship will be considered as an AE reported, but will be considered as not reported for the severity or relationship. For example, an AE with missing severity will be considered as an AE reported for the analysis of any grade, but will be considered as not reported for the analysis of at least grade 3. The analysis of solicited AEs will include the safety data as documented by the investigator.

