### 4. POPULATIONS (ANALYSIS SETS) FOR ANALYSIS

Analysis Sets	Description
All screened participants (ALL)	The “all screened participants” set includes all participants that were screened, regardless of whether they were enrolled and/or randomized.

Analysis Sets	Description
All randomized participants (ALL RANDOMIZED)	The “all randomized participants” set includes all participants that were randomized to one of the treatment groups.
Full Analysis Set (FAS)	The full analysis set (FAS) includes all participants with a vaccine administration documented.
Per-protocol Influenza Immunogenicity (PPII) Set	
Per Protocol Influenza Immunogenicity (PPII) Set: All randomized participants who received Ad26.COV2.S vaccine in combination with a seasonal influenza vaccine for the coadministration group and those who received a seasonal influenza vaccine alone for the control group, for whom immunogenicity data are available for at least one of the influenza strains in the vaccine.
 
PPII set will include participants who have received a complete primary vaccination with an authorized/licensed COVID-19 vaccine as well as COVID-19 vaccine-naïve participants.
 
Samples taken after (but not before) a participant experienced a confirmed major protocol deviation expected to impact the immunogenicity outcomes will be excluded from the PPII analysis.
 
The primary analysis set for analyses related to influenza immunogenicity is the PPII Set. As a sensitivity analysis, key tables may also be based on the FAS.

Per-Protocol SARS-CoV-2 Immunogenicity (PPSI) Set	
The per protocol SARS-CoV-2 Immunogenicity Set (PPSI) will include all randomized participants who received Ad26.COV2.S vaccine in combination with seasonal influenza vaccine for the co-administration group and Ad26.COV2.S vaccine alone for the control group, and for whom immunogenicity data are available.
 
PPSI set will be restricted to participants who have received a complete primary vaccination with an authorized/licensed COVID-19 vaccine.
 
N seronegative participants at day 1 that became N serology positive during the study will be excluded for analyses of future timepoints.
 
Participants with positive molecular test for SARS-CoV-2 will also be excluded from future timepoints.
 
Samples taken after a participant meets the criteria for a major protocol deviation expected to impact the immunogenicity outcomes will be excluded from the PPSI analysis.

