## **5.6.1. Adverse Events**

### **5.6.1.1. Definitions of Adverse Events Endpoints**

Solicited AEs shown in the tables are extracted from the investigator assessment pages (CE) of the CRF. For unsolicited AEs, only the AEs within the 28-day period following each vaccination will be presented in the safety tables except for SAE, MAAEs and AESI cases which will be captured and tabulated in the outputs covering the whole study period.

Local solicited AEs symptoms will be by definition considered as related to the study vaccine.

The severity of the AEs will be classified as toxicity grade 1 to 4 (refer to appendix 7). Solicited events of grade 0, not reported in the CE domain, will therefore not be reported in the AE analysis.

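### Vaccinated participants with no solicited-event assessment after a dose count as symptom-free, so any such gap lowers the reported reactogenicity rates and can shift the group contrast in either direction

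*SAP*

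**What the plan says.** Five statements in the SAP combine to give the counting rule for solicited events.

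- **Non-report (5.6.1.4):** "Participants who do not report an event will be considered as participants without an event". The same paragraph opens with "Missing data will not be imputed".
- **Denominator (5.6.1.2):** "Denominator for the percentages is the number of participants in the considered population and phase for a certain regimen".
- **Population (5.6.1.2 and 4):** "Safety analyses will be performed on the FAS", and "The full analysis set (FAS) includes all participants with a vaccine administration documented". Membership does not depend on having any solicited data. Protocol 9.4.5 also bases safety on the FAS and sets no other rule.
- **Source (5.6.1.1):** "Solicited AEs shown in the tables are extracted from the investigator assessment pages (CE) of the CRF".
- **Grade 0 (5.6.1.1):** "Solicited events of grade 0, not reported in the CE domain, will therefore not be reported in the AE analysis".

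I found in neither document a denominator of participants with solicited data, a planned report of diary or assessment completeness, or a sensitivity analysis for missing solicited data. The Safety row in the SAP table of analysis sets cannot be read reliably in the copy available, so I draw nothing from it; SAP 5.6.1.2 names the FAS directly.

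**The concern.** Solicited events are actively asked about over a fixed 7-day period, so not assessed and assessed with no symptom are different results. In the analysis source neither leaves a record, and the rule scores both as no event. In effect that imputes a non-event, in a paragraph that says nothing is imputed.

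Reactogenicity of Ad26.COV2.S given separately or together with influenza vaccine is a secondary objective for both influenza doses. Ad26.COV2.S is given on Day 1 in the co-administration (CoAd) groups and on Day 29 in the control groups. A comparison of Ad26.COV2.S with and without influenza vaccine therefore sets a post-dose 1 rate against a post-dose 2 rate. Randomization does not make completeness equal across two different visits. What is at stake is the accuracy of the tabulated rates and of that descriptive contrast.

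**Working it through.** The plan states no missing-diary rate and no precision target for solicited events, so there is no figure of its own to reproduce. The check follows the counting rule.

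**Inputs**
- Illustrative rates, protocol Table 1 (Ad26.COV2.S, N = 3,356): injection site pain 1634/3356 = 48.69%, which agrees with the printed 48.7%; fever 302/3356 = 9.0% (printed as 9.1%).
- Group size for scale: about 305 per standard-dose group (protocol 9.2).
- Missing fraction m, the share of vaccinated participants with no solicited assessment after that dose: **assumed**, shown over a range.

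**Single rate.** Let p be the rate in participants with data. The rule gives p × (1 − m). If missingness is unrelated to symptoms, the shortfall is p × m.

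| Assumed m | Participants of 305 | Pain, under the rule | Shortfall (points) | Fever, under the rule | Shortfall (points) |
|---|---|---|---|---|---|
| 2% | about 6 | 48.69 × 0.98 = 47.7% | 0.97 | 8.8% | 0.18 |
| 5% | about 15 | 48.69 × 0.95 = 46.3% | 2.43 | 8.5% | 0.45 |
| 10% | about 30 | 48.69 × 0.90 = 43.8% | 4.87 | 8.1% | 0.90 |

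**Contrast, CoAd post-dose 1 minus control post-dose 2.** The rule gives p1(1 − m1) − p2(1 − m2).
- Equal true rates of 48.69%, m1 = 5%, m2 = 10%: 48.69 × (0.10 − 0.05) = +2.4 points.
- The same rates with m1 = 10%, m2 = 5%: −2.4 points.
- A true difference of +10.0 points (58.69% versus 48.69%) with 5% missing in both: 10.0 × 0.95 = +9.5 points. Equal missingness leaves the ratio unchanged and shrinks the difference.
- The same true difference with m1 = 15%, m2 = 5%: 58.69 × 0.85 − 48.69 × 0.95 = 49.89 − 46.26 = +3.6 points.

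**Dependence on why data are missing.** Let participants without data have a true rate of r × p. The true overall rate is p(1 − m) + m × r × p.
- Error of the SAP rule: −m × r × p. It is never upward, and it is zero only if m = 0 or r = 0.
- Error of a denominator restricted to participants with data: +m × (1 − r) × p. It is zero at r = 1 and upward if non-reporters had fewer symptoms.
- The two errors are equal in size at r = 0.5. At m = 5% and p = 48.69%, each is 0.05 × 0.5 × 48.69 = 1.2 points, in opposite directions. Above r = 0.5 the restricted denominator is closer to the truth.

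**The case against.** The strongest reply is that few participants will be wholly unassessed. The tables use the investigator's assessment rather than the raw diary, and the protocol gives several chances to make that assessment: on-site observation of at least 15 minutes, a site contact about 7 days after each dose, an investigator's reactogenicity assessment after each dose, further diary review if symptoms continue, and a Day 29 step to resolve missing solicited data. The post-dose 2 period starts at the second vaccination (SAP 5.1.2), so those who miss it do not enter that denominator. All this stands and makes m smaller. It does not change how the remaining participants are counted, and it does not tell the reader how many there were.

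Second, the SAP says that grade 0 is absent from the analysis domain; it does not say that completion of the assessment page or diary goes unrecorded, and table detail is left to a Data Presentation Specification that is not available here. That is fair, but the denominator in SAP 5.6.1.2 is explicit and makes no use of such information.

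Third, the size is assumed. A reader might infer that reactogenicity will be understated by a known amount, or that the control rate will be diluted more because Ad26.COV2.S comes second there. With 2% missing after dose 1 and 10% after dose 2, equal rates of 48.7% would differ by 47.7 − 43.8 = 3.9 points. The documents support neither inference. They give no missing rate and do not say that completion is lower after dose 2. The Day 29 check can recover dose 1 data and I found no matching instruction after dose 2, but that does not show what completion will be. Pain is also the most frequent event and only an arithmetic example: CoAd participants receive two active injections on Day 1 and controls one injection on Day 29, so equal true rates are not expected.

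Fourth, the comparison is descriptive and the rule is prespecified and the same in every group. Both are true. They limit the consequence, but a common rule does not give a common bias if missingness differs.

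**Conclusion.** The point holds in conditional form. As written, the SAP scores a vaccinated participant with no solicited assessment after a dose as event-free. If there are any, each solicited rate is reduced by the factor (1 − m). With none, there is no bias.

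For a 48.7% event the reduction is about 1.0, 2.4 and 4.9 points at 2%, 5% and 10% missing; for a 9.0% event it stays below 1 point over that range. These sizes rest on assumed missing fractions and on missingness unrelated to symptoms. The bias in a single rate is downward or nil. The bias in the contrast between CoAd post-dose 1 and control post-dose 2 has no predictable sign.

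This is a minor point on a secondary, descriptive objective. It leaves the primary non-inferiority conclusions unaffected.

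**What to change.** Amend SAP 5.6.1.2 and 5.6.1.4 for solicited events only:

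- **Denominator:** for each dose, vaccinated participants with a completed investigator reactogenicity assessment, or at least one day of diary data, in the 7 days after that dose.
- **Completeness:** report the number of vaccinated participants without such data, by group and dose.
- **Sensitivity analysis:** keep the present FAS denominator, because the new one assumes that missingness is unrelated to symptoms.
- **Unsolicited events:** leave the rule unchanged, since participants are not specifically questioned about them in the diary.

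The cost is a short SAP edit, one extra table and slightly higher reported solicited rates. Diary entries already go to the sponsor electronically (protocol 8.3.2), so the diary part needs no new collection. One limit remains: a participant with a single diary day still counts as event-free for the days not recorded, so the change deals with wholly missing assessments and not with partial diaries.
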